#### 6.6.4 Children’s Depression Inventory 2nd Edition Self-Report Short Version (CDI 2:SR[S])

The Children’s Depression Inventory (CDI) is a widely used pediatric self-report depressive symptoms assessment in clinical trials ([Myers & Winters 2002](#)). It is a comprehensive assessment of depressive symptoms in youth ages 7 to 17 years. The second edition of the CDI Self-Report (CDI 2:SR) contains 28 items to cover the age-appropriate depressive symptoms which cover affective, cognitive, motivational, neurovegetative, and secondary impairment domains. It covers the criterion symptoms of major depressive disorder and dysthymic disorder as operationalized in the DSM-IV. The CDI 2:SR[S] ([Appendix 9](#)) is the short form of CDI 2:SR. It contains 12 items and takes about half the time of the full-length version to administer (5–10 minutes). The short report form covers primarily affective, cognitive, and neurovegetative aspects of depression. It has been shown that the Total Score of the CDI 2:SR[S] is highly correlated to a Total Score on the selected items of the full-length version ([Kovacs 2011](#)). Due to its brevity, the CDI 2:SR[S] is a suitable screening assessment; however, this scale is not validated in pediatric patients with narcolepsy. Many narcolepsy symptoms overlap with items assessed in the CDI 2:SR[S], e.g., feeling tired, not having fun (in order to control cataplexy attacks); therefore, this scale is used only as a screening assessment for the risk of depression in this study.

#### 6.6.5 Multidimensional Anxiety Scale for Children 10-item (MASC-10)

The MASC-10, a short version of the MASC, is a multidimensional measure with ten items that combine the basic anxiety scales from the long version to produce one score that

Xyrem® (sodium oxybate) oral solution  
Clinical Study Protocol: 13-005 Amendment 5

Jazz Pharmaceuticals

indicates the severity of anxiety problems ([Appendix 10](#)). Satisfactory test-retest reliability was demonstrated for this instrument ([March 1997](#), [March & Sullivan 1999](#)).

#### 6.6.6 Cataplexy Frequency Diary

The subject (if needed, with the help of caregiver) will complete a cataplexy frequency diary ([Appendix 11](#)) daily in the evening during Part 1 to record the daily frequency of the subject's cataplexy attacks ([Appendix 1](#) and [Appendix 2](#)).

#### 6.6.7 Clinical Global Impression of Severity (CGIs) Questionnaires

Clinical Global Impression of Severity (CGIs) is a 7-point Likert rating scale and is a widely used assessment in clinical psychopharmacology trials to assess severity of illness. The responses of this investigator-completed scale range from 1 = normal, no signs of illness, to 7 = among the most extremely ill patients. Using the questionnaires described below, Investigators will rate their impression of the severity of the subject's condition before the subject received any narcolepsy treatment (historical) and the severity of the subject's current condition at specified times during Part 1 of the study.

##### 6.6.7.1 CGIs for Historical Narcolepsy Overall Severity Prior to any Narcolepsy Treatment

At Part 1 Screening (Visit 1), Investigators will rate their impression of the severity of the subject's narcolepsy overall prior to any narcolepsy treatment ([Appendix 15](#)).

##### 6.6.7.2 CGIs for Historical Cataplexy Severity Prior to any Narcolepsy Treatment

At Part 1 Screening (Visit 1), Investigators will rate their impression of the severity of the subject's cataplexy prior to any narcolepsy treatment ([Appendix 16](#)).

##### 6.6.7.3 CGIs for Narcolepsy Overall (current condition)

Investigators will rate their impression of the subject's current severity of narcolepsy overall at the following time points: Part 1 Screening (Visit 1), the start of the Stable-Dose Period (Visit 2 [for subjects on Xyrem at study entry]) or beginning of titration (Visit 1.1 [for Xyrem-naïve subjects]) and the end of the Stable-Dose Period (Visit 3) ([Appendix 17](#)).

##### 6.6.7.4 CGIs for Cataplexy Severity (current condition)

Investigators will rate their impression of the subject's current cataplexy severity at the following time points: Part 1 Screening (Visit 1), the start of the Stable-Dose Period (Visit 2 [for subjects on Xyrem at study entry]) or beginning of Part 1 titration (Visit 1.1 [for Xyrem-naïve subjects]) and the end of the Stable-Dose Period (Visit 3) ([Appendix 18](#)).

#### 6.6.8 Patient Global Impression of Change (PGIc) for Narcolepsy Overall

At the end of the Double-Blind Treatment Period (Visit 4), the subject (if needed, with the help of caregiver) will rate his/her narcolepsy overall since the last visit (Visit 3 [end of Stable-Dose Period]) on a 7-point scale ranging from "very much better" to "very much worse" ([Appendix 19](#)). If the subject discontinues during the Double-Blind Treatment Period, he/she will complete the PGIc at Part 1 early termination.

### 6.6.9 Clinician Global Impression of Change (CGIc) for Narcolepsy Overall and for Cataplexy Severity

At the end of the Double-Blind Treatment Period (Visit 4), Investigators will rate their impression of any change in the severity of the subject's narcolepsy overall ([Appendix 20](#)) and their impression of any change in the severity of the subject's cataplexy ([Appendix 21](#)) since the start of the Double-Blind Treatment Period on a 7-point scale ranging from "very much improved" to "very much worse." If the subject discontinues during the Double-Blind Treatment Period, the Investigator will complete the CGIc for narcolepsy overall and for cataplexy severity at Part 1 early termination.

### 6.6.10 Dosing Diaries

Electronic Dosing Diaries will be used to capture both study drug doses taken and, if applicable, stimulant doses taken during Part 1.

#### 6.6.10.1 Study Drug Dosing Diary

The subject (if needed, with the help of caregiver) will complete the Study Drug Dosing Diary ([Appendix 12](#)) each morning, from the Part 1 Screening Visit (Visit 1) for the subjects on Xyrem at study entry and from the start of the Part 1 Open-Label Titration Period (Visit 1.1) for Xyrem-naïve subjects through the end of Part 1 of the study. The diary is completed to capture if the first and second doses of study drug were taken the night before.

#### 6.6.10.2 Stimulant Dosing Diary

The subject (if needed, with the help of caregiver) will complete the Stimulant Dosing Diary ([Appendix 13](#)) each evening, from the Part 1 Screening Visit (Visit 1) for the subjects on Xyrem at study entry and from the start of the Part 1 Open-Label Titration Period (Visit 1.1) for Xyrem-naïve subjects through the end of the Double-Blind Treatment Period. The diary is completed to capture if the regular dose of stimulants was taken that day, if the subject is taking stimulants.

### 6.6.11 School Attendance Diary

The School Attendance Diary will be completed if the subject has school during the last 2 weeks of the Stable-Dose Period and during the Double-Blind Treatment Period. The subject (if needed, with the help of caregiver) will record daily in the diary if the subject had a scheduled school day and if the subject missed the school day because of narcolepsy ([Appendix 14](#)).

### 6.6.12 Plan of referral

The Investigator should have a plan to refer for appropriate care or to provide appropriate care for subjects requiring emergent medical and/or psychiatric care during the course of study participation.

## 6.7 12-Lead Electrocardiogram (ECG)

A standard 12-lead ECG will be recorded with the subject resting supine for at least 5 minutes at Part 1 Screening (Visit 1), the End of the Double-Blind Treatment Period (Visit 4), and the final Part 1 visit (Visit 15) or Part 1 early termination.

## 6.8 Polysomnography (PSG)

A PSG will be performed on PSG nights according to a standard protocol, which will be provided in a manual to each site, at the times specified in the schedules of events. The manual will include all parameters to be recorded, methods, and a scoring appendix. Oxygen saturation will be monitored according to the study center's standard procedures. Cardiac rhythm strips (over 30 seconds), closest to the specified time points with minimum artifact, will be extracted from the PSG data by the core lab.

Standard PSG parameters will be recorded. The PSG parameters of interest include:

- Apnea Index (AI) and Apnea Hypopnea Index (AHI)
- SpO2 (mean and nadir)

EtCO2 or TcCO2 will be recorded at sites where monitoring is routinely performed, provided it does not negatively impact participation or PSG data integrity. In addition, cardiac rhythm strips (30 seconds) will be obtained at 1 h, 4 h (pre-2nd dose), 5 h, and 8 h after the first Xyrem dose for subjects on Xyrem during the PSG.

**Study Personnel on PSG Nights:** A physician, either the Investigator or a Sub-investigator, must be on call and be readily available during PSG nights. An experienced sleep technologist must be present to monitor the PSG during PSG nights.

**Multiple Sleep Latency Test (MSLT):** If the subject has never been diagnosed with narcolepsy with cataplexy and meets all ICSD-3 Type 1 narcolepsy criteria A and B1 at Part 1 Screening other than the MSLT, an MSLT can be conducted during Part 1 Screening, with the permission of the Medical Monitor, to confirm the diagnosis of narcolepsy with cataplexy.

The ICSD-3 diagnostic criteria for narcolepsy with cataplexy are as follows (Type 1, the International Classification of Sleep Disorders 3rd Revised Diagnostic and Coding Manual [ICSD-3]) ([American Academy of Sleep Medicine 2014](#)):

- **Type 1** (hypocretin deficiency syndrome, narcolepsy-cataplexy, narcolepsy with cataplexy):
  - Criteria A and B must be met:**
    - A. Daily periods of irrepressible need to sleep or daytime lapses into sleep for  $\geq 3$  months.
    - B. The presence of one or both of the following:
      1. Cataplexy *and* a mean sleep latency of  $\leq 8$  minutes and two or more sleep onset REM periods (SOREMPs) on an MSLT performed according to standard techniques. A SOREMP (within 15 minutes of sleep onset) on the

Xyrem® (sodium oxybate) oral solution  
Clinical Study Protocol: 13-005 Amendment 5

Jazz Pharmaceuticals

---

preceding nocturnal polysomnogram may replace one of the SOREMPs on the MSLT.

2. CSF hypocretin-1 concentration, measured by immunoreactivity, is either  $\leq 110$  pg/mL or  $< 1/3$  of mean values obtained in normal subjects with the same standardized assay.

## 6.9 Clinical Laboratory Tests

### 6.9.1 Laboratory Parameters

Blood and urine samples for laboratory tests will be collected at times indicated in the Schedules of Events ([Appendix 1](#), [Appendix 2](#), [Appendix 22](#), [Appendix 23](#), and [Appendix 24](#)).

Subjects will be in a seated or supine position during blood collection. Clinical laboratory tests will include the following:

Xyrem® (sodium oxybate) oral solution  
Clinical Study Protocol: 13-005 Amendment 5

Jazz Pharmaceuticals

**Table 2 List of Laboratory Tests**

Hematology:	Serum Chemistry:
- Complete blood count (CBC)	- Albumin (ALB)
Urinalysis:	- Alkaline phosphatase (AP)
- Protein	- Alanine aminotransferase (ALT; SGPT)
- Glucose	- Aspartate aminotransferase (AST; SGOT)
- Bilirubin	- Blood urea nitrogen (BUN)
- pH	- Calcium (Ca)
- Nitrite	- Carbon dioxide (CO 2 )
- Ketones	- Chloride (Cl)
- Urobilinogen	- Creatinine
- Occult blood	- Creatine kinase
- Leukocyte esterase	- Gamma-glutamyl transferase (GGT)
Microscopic examination for blood, all types of cells and casts.	- Globulin
Serum and urine human chorionic gonadotropin (hCG) (only for females who have reached menarche)	- Glucose
HLA DQB1:0602 haplotype (at Part 1 Screening only, for subjects with no previous documented results available)	- Lactate dehydrogenase (LDH)
Tests of growth and precocious puberty:	- Phosphorus
- Growth hormone (GH)	- Potassium (K)
- Insulin-like growth factor-1 (IGF-1, low sensitivity)	- Sodium (Na)
- Prolactin	- Total bilirubin
- Luteinizing hormone (LH)	- Direct bilirubin
- Follicle Stimulating Hormone (FSH)	- Total cholesterol
- Testosterone	- Total protein
- Estradiol	- Triglycerides
	- Uric acid
	Coagulation (within 30 days prior to PK Night 1 for PK subjects only):
	- Prothrombin time (PT)/International normalized ratio (INR)
	- Activated partial thromboplastin time (PTT)
	Thyroid Function
	- Thyroid stimulating hormone (TSH) (at Part 1 Screening only)

The clinical laboratory tests will be performed at a central or local laboratory. An authorized back-up laboratory, as indicated on the Form FDA 1572 or equivalent, may be used if necessary as an emergency laboratory. The Investigator will supply Jazz Pharmaceuticals or its designee with the back-up laboratory's current licensure and laboratory reference ranges.

Please note exclusionary clinical laboratory parameters listed in the exclusion criteria. In addition, any laboratory parameter that is out of range and considered clinically significant (as determined by the Investigator) at the end of treatment must be re-evaluated. The

Xyrem® (sodium oxybate) oral solution  
Clinical Study Protocol: 13-005 Amendment 5

Jazz Pharmaceuticals

---

Investigator will provide an explanation of all clinically significant observations. These findings will be reported as AEs.

#### 6.9.1.1 Pregnancy Test

Pregnancy tests will be performed for female subjects who have reached menarche. At Part 1 Screening (Visit 1), the end of the Double-Blind Treatment Period (Visit 4), and Part 2 Screening, a serum pregnancy test will be performed. A urine pregnancy test will be performed at the start of the Part 1 Open-Label Titration Period for Xyrem-naïve subjects (Visit 1.1), at the start of the Stable-Dose Period for subjects previously on Xyrem (Visit 2), and at the final Part 1 visit (Visit 15) or Part 1 early termination ([Appendix 1](#) and [Appendix 2](#)). During Part 2, a urine pregnancy test will be performed at Visit 18 (for re-enrollers only), at every 6-month visit (Visits 24, 30, and 36), and at Part 2 Study Termination/Part 2 Early Termination (Visit 42) ([Appendix 22](#), [Appendix 23](#), and [Appendix 24](#)).

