3.1.5 Open-Label Safety Period (to allow up to 1 year Xyrem exposure)

Subjects who are eligible to participate in the Open-Label Safety Period will participate in this period for 47 weeks if they entered the study on a stable dose of Xyrem or for a period of 38-45 weeks if they entered as Xyrem naïve, depending on the duration of the titration period in which they participated (45 weeks assumes that the shortest titration period will be 3 weeks for those subjects who reach an optimal response very quickly during titration).

All study procedures and assessments will be carried out according to the planned schedule (changes in Xyrem dose will generally not affect the schedule).

All subjects will be seen in the clinic 4 weeks after the Open-Label Safety Period begins (Visit 5) and then at Weeks 18, 26, 39, and 52 from study entry (Day 1). However, if in the case of subjects who are Xyrem naïve, Visit 5 is within 2 weeks of the Week 18 visit, the first clinic visit of the Open-Label Safety Period will be the Week 18 visit.

Subjects/parent(s)/guardian(s) will be contacted in the interim by phone at Weeks 16, 22, 30, 34, 43, and 48 from study entry (Day 1). A final PSG will be performed at Week 52 or the Part 1 early termination visit (if the subject who terminates early is willing to participate in another PSG night and if they are willing to take Xyrem the evening of the PSG). The Part 1 early termination PSG does not apply for subjects who discontinue before entering the Open-Label Safety Period. Clinicians may schedule clinic or phone visits between protocol-specified clinic visits to ensure subject safety or to accommodate PK visits (if applicable). Additional drug dispensing visits may be added as required by local law or at the Investigator's discretion based on safe drug storage requirements. Stimulants for EDS may be used as adjunctive therapy throughout the trial, and can be adjusted or discontinued as appropriate.

For subjects who had entered the Double-Blind Treatment Period before Amendment 4 was effective, upon entering the Open-Label Safety Period, these subjects will be started at a dose no higher than half the Xyrem dose they received at the end of the Stable-Dose Period or the

Xyrem® (sodium oxybate) oral solution  
Clinical Study Protocol: 13-005 Amendment 5

Jazz Pharmaceuticals

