#### 6.9.1.2 Drug and Alcohol Screen

At Part 1 Screening (Visit 1), the beginning of the Part 1 Open-Label Titration Period for Xyrem-naïve subjects (Visit 1.1), the start of the Stable-Dose Period for subjects previously on Xyrem (Visit 2), the end of the Double-Blind Treatment Period (Visit 4), and during the Open-Label Safety Period at Visits 5, 7, 9, 12, and 15 ([Appendix 1](#) and [Appendix 2](#)), an alcohol test and a panel of urinary drug screens will be performed. During Part 2, an alcohol test and a panel of urinary drug screens will be performed at Part 2 Screening, at Visit 18 (for re-enrollers only), at every 6-month visit (Visits 24, 30, and 36), and at Part 2 Study Termination/Part 2 Early Termination (Visit 42) ([Appendix 22](#), [Appendix 23](#), and [Appendix 24](#)). The panel of urinary drug screens will test for the following prohibited substances. (A positive amphetamine result will not exclude a subject who is taking prescribed amphetamines.)

- Amphetamine (not prescribed)
- Barbiturates
- Benzodiazepines
- Cannabinoids
- Cocaine
- Opiates

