## 6.14 Removal of Subjects from the Study or Study Drug

All subjects are free to withdraw from participation in this study at any time, for any reason, and without prejudice. The Investigator must withdraw any subject from the study if the subject or subject's parent(s)/guardian(s) requests to stop participating in the study.

The Investigator, Jazz Pharmaceuticals or its designee may remove a subject from the study at any time and for any reason.

If any of the criteria below are met during the study, study drug administration must be stopped and the subject discontinued from the study.

- Suicide risk reported or assessed by C-SSRS
- Clinically significant depression independent of narcolepsy symptoms
  - If the T-score is  $\geq 65$  on CDI 2SR[S], an evaluation of depression by the Investigator (if qualified as a mental health professional) or by the Investigator in consultation with a mental health professional must be performed to exclude clinically significant depression
- Any PSG parameters that indicate, in the judgment of the Investigator, a risk to the subject's safe continued participation
- Subject becomes pregnant
- A positive urine drug screen for benzodiazepines or drugs of abuse (if the subject takes prescribed amphetamines, a positive result for amphetamines will not exclude the subject) or any suspicion by the investigator of abuse or diversion of study drug
- A positive alcohol test
- 3-fold or greater elevation above the upper limit of normal (ULN) of alanine aminotransferase (ALT) or aspartate aminotransferase (AST) accompanied by an elevation of serum total bilirubin greater than two times the ULN
- Liver enzyme (AST, ALT) value greater than or equal to 5 times the ULN
- Experiences an intolerable AE that is related to the study drug and/or procedure
- Develops any clinically significant worsening in narcolepsy symptoms during the Stable-Dose Period
- Develops a clinically significant laboratory or ECG abnormality that is related to the study drug and/or procedure
- Requires a medication that is prohibited by the protocol, with the exception of short-term opioid or benzodiazepine use (see [Section 5.7](#))
- Does not follow guidelines or procedures specified in the protocol

Xyrem® (sodium oxybate) oral solution  
Clinical Study Protocol: 13-005 Amendment 5

Jazz Pharmaceuticals

- 
- Is lost to follow-up
  - Does not continue to meet certain entry criteria or meets certain exclusion criteria during the course of the study

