### 7.4.1 Visit 5 (4 weeks after end of the Double-Blind Treatment Period) and Visits 7, 9, 12 (Weeks 18, 26, 39 from Day 1)

- Record height and weight in ordinary indoor clothes (without shoes).
- Obtain vital signs (systolic and diastolic blood pressure, pulse/heart and respiratory rate, and body temperature) after the subject has been resting for at least 5 minutes.
- Perform urine drug and alcohol test screens.
- Review Cataplexy Frequency Diary.
- Review Study Drug Dosing Diary.
- Administer the following:
  - ESS (CHAD) ([Appendix 6](#))
  - SF-10 ([Appendix 7](#))
  - C-SSRS ([Appendix 8](#); Since Last Visit version for subjects  $\geq 12$  years of age and Children's Since Last Visit version for subjects  $< 12$  years of age)
  - CDI 2:SR[S] ([Appendix 9](#))
  - MASC-10 ([Appendix 10](#))
- Record all AEs on the AE CRF.
- Record all concomitant medications on the concomitant medications CRF.
- Collect study drug dispensed at the previous visit and measure compliance.
- Dispense study drug. (Access IVRS/IWRS.) Provide instructions for dose administration and, if flavored diluent is requested and available, the preparation of study drug with flavored diluent to subjects/parent(s)/guardian(s). See [Section 6.10](#).
- Schedule the next clinic or phone visit

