#### 7.5.3 Visits 21, 27, 33, and 39 (Onsite)

- Record height and weight in ordinary indoor clothes (without shoes).

Xyrem® (sodium oxybate) oral solution  
Clinical Study Protocol: 13-005 Amendment 5

Jazz Pharmaceuticals.

- 
- Obtain vital signs (systolic and diastolic blood pressure, pulse/heart and respiratory rate, and body temperature) after the subject has been resting for at least 5 minutes.
  - Record all AEs on the AE CRF.
  - Record all concomitant medications on the concomitant medications CRF.
  - Collect study drug dispensed at the previous visit and measure compliance.
  - Dispense study drug. (Access IRT.) Provide instructions for dose administration and, if flavored diluent is requested and available, the preparation of study drug with flavored diluent to subjects/parent(s)/guardian(s). See [Section 6.10](#).
  - Determine when the subject will be 18 years of age. Schedule the Part 2 Study Termination Visit to occur *prior to* the subject's 18th birthday.

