#### 7.5.4 Visits 24, 30, and 36 (Onsite)

- Record height and weight in ordinary indoor clothes (without shoes).
- Perform alcohol test and urine drug screens.
- Obtain urine sample for pregnancy test (only perform for female subjects who have reached menarche).
- Obtain vital signs (systolic and diastolic blood pressure, pulse/heart and respiratory rate, and body temperature) after the subject has been resting for at least 5 minutes.
- Record all AEs on the AE CRF.
- Record all concomitant medications on the concomitant medications CRF.
- Collect study drug dispensed at the previous visit and measure compliance.
- Dispense study drug. (Access IRT.) Provide instructions for dose administration and, if flavored diluent is requested and available, the preparation of study drug with flavored diluent to subjects/parent(s)/guardian(s). See [Section 6.10](#).
- Determine when the subject will be 18 years of age. Schedule the Part 2 Study Termination Visit to occur *prior to* the subject's 18th birthday.

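### Part 1 schedules no pregnancy test for 38 to 47 weeks on open-label drug, although pregnancy is a mandatory stop; one urine test at Visit 9 would cut the longest interval to 26 weeks

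*Protocol*

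**What the plan says.** Protocol Section 6.9.1.1 sets the Part 1 tests for girls who have reached menarche: serum at Visit 1; urine at Visit 1.1 (naïve) or Visit 2 (on Xyrem at entry); serum at Visit 4; and urine "and at the final Part 1 visit (Visit 15) or Part 1 early termination". Appendices 1.1, 2.1 and 2.2 mark the same visits. Section 7.4.1 (clinic Visits 5, 7, 9 and 12) and Section 7.4.2 (phone visits) list no pregnancy test.

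Visit 4 to Visit 15 is the Open-Label Safety Period. Under Section 3.1.5, subjects "participate in this period for 47 weeks if they entered the study on a stable dose of Xyrem"; naïve subjects stay in it for 38 to 45 weeks, depending on the length of titration.

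Section 6.14 lists "Subject becomes pregnant" among the criteria that require study drug to be stopped and the subject discontinued.

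The urine drug screen runs more often. Section 6.9.1.2 places it "during the Open-Label Safety Period at Visits 5, 7, 9, 12, and 15", and Section 7.4.1 repeats the instruction: "Perform urine drug and alcohol test screens".

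In Part 2, Section 6.9.1.1 schedules a urine pregnancy test "at every 6-month visit (Visits 24, 30, and 36") and again at Visit 42. Section 7.5.3 lists none for the other quarterly clinic visits (21, 27, 33 and 39).

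**The concern.** A mandatory stopping rule works only as well as the means of finding out that it has been met. For most of Part 1 on open-label drug, no scheduled test can show that a girl is pregnant. A girl who reaches menarche after Visit 4 would have no scheduled test at all until Visit 15 or early termination.

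Two features of the protocol make the gap stand out. First, drug screens and pregnancy tests fall on the same visits everywhere else: Visit 1, Visit 1.1 or 2, Visit 4, Visit 15, Part 2 Screening, and Visits 18, 24, 30, 36 and 42. They part only at Visits 5, 7, 9 and 12, where the screen is done and the pregnancy test is not. Second, Part 2 keeps a 6-monthly pregnancy test even for subjects who continue directly from Part 1 and have no further laboratory blood samples or ECG.

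At stake is the safety of post-menarcheal girls: a pregnancy could continue on study drug for weeks to months unless suspicion prompts an unscheduled test.

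**Working it through.** This is calendar arithmetic on the nominal weeks in the protocol.

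**Inputs**
- Visit 4: Week 5 for subjects on Xyrem at entry (Section 7.1.5); Week 14 for naïve subjects after a 10-week titration (Section 7.2.5).
- Shortest titration assumed: 3 weeks (Section 3.1.5). With 2 weeks of stable dose and 2 weeks of the Double-Blind Period, Visit 4 then falls at Week 3 + 2 + 2 = 7.
- Visits 5, 7, 9 and 12: Weeks 9, 18, 26 and 39 for subjects on Xyrem at entry (Appendix 1.1).
- Visit 15: Week 52. Visits 9 and 15 each have a window of ±7 days.

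**Current gap = 52 − week of Visit 4**
- On Xyrem at entry: 52 − 5 = 47 weeks.
- Naïve, 10-week titration: 52 − 14 = 38 weeks.
- Naïve, 3-week titration: 52 − 7 = 45 weeks.

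These reproduce the period lengths in Section 3.1.5. A Visit 15 one week late stretches the 47 weeks to 48.

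**With a test added at Visit 9, the two gaps are 26 − (week of Visit 4) and 52 − 26**
- On Xyrem at entry: 21 and 26 weeks.
- Naïve, 10-week titration: 12 and 26 weeks.
- Naïve, 3-week titration: 19 and 26 weeks.

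The longest is 26 weeks, or 26 + 2 = 28 if both windows are used in full. The 6-month spacing of Part 2 is also 26 weeks, and 28 with ±7 days at both ends.

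**Why Visit 9.** For a subject on Xyrem at entry, one added test leaves a longest gap of:
- Visit 5: max(4, 43) = 43 weeks
- Visit 7: max(13, 34) = 34 weeks
- Visit 9: max(21, 26) = 26 weeks
- Visit 12: max(34, 13) = 34 weeks

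Visit 12 does slightly better only after the longest titrations (10 weeks: max(25, 13) = 25), so Visit 9 is the best single choice across groups.

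**Illustrative mean wait to the next scheduled test.** If conception is equally likely at any time in the period, the mean wait is Σ(gap²) / (2 × Σ gap).

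| Group | Now | With Visit 9 |
|---|---|---|
| On Xyrem at entry | 47/2 = 23.5 weeks | (441 + 676)/94 = 11.9 weeks |
| Naïve, 10-week titration | 38/2 = 19.0 weeks | (144 + 676)/76 = 10.8 weeks |
| Naïve, 3-week titration | 45/2 = 22.5 weeks | (361 + 676)/90 = 11.5 weeks |

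**The case against.** **The protocol is consistent.** A reader might infer that the stopping rule and the test schedule contradict each other. They do not: Section 6.9.1.1, Section 7.4.1 and the appendices agree, and a stopping rule can be met by any route of discovery. Nor is the spacing special to pregnancy. Liver enzymes and ECG, which also carry stopping criteria, are scheduled in Part 1 at Visits 1, 4 and 15 only. This stands; the point is one of design choice.

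**The 6-month benchmark is inferred.** The protocol nowhere states that 6 months is the longest acceptable interval. In Part 2 the pregnancy tests fall on the drug-screen visits, so the interval may reflect how visits were bundled, and the same girls are older by then. This stands too. The benchmark is what the protocol itself does under the same rule, and no more. For the same reason, tests at Visits 5, 7 and 12 as well would be denser than Part 2, and the document gives no ground for asking for them.

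**There are other controls.** Contraception or abstinence is required for the study plus 30 days (Section 4.2). Weight and vital signs are recorded at Visits 5, 7, 9 and 12, and there are six phone contacts. That makes up to ten contacts, and for subjects on Xyrem at entry at most 7 weeks pass between them (Weeks 9 to 16). Extra safety visits are allowed (Section 3.1.5), and a known pregnancy must be reported within 24 hours (Section 6.12.1.3). These mitigate the gap but do not replace a test: the contraception criterion is willingness at entry, adverse-event questioning avoids specific symptoms (Section 6.12.1), and the reporting duty starts only once the pregnancy is known.

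**The harm is not quantified.** The protocol states no embryo-fetal risk for sodium oxybate and does not give the number of post-menarcheal girls. At Amendment 5, few girls may still be short of Visit 9. This limits the size of the point, although Section 3.1.8 does expect subjects still ongoing in the study when that amendment takes effect.

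**Conclusion.** The point holds as a modest safety improvement. Part 1 has no scheduled pregnancy test for 47 weeks (on Xyrem at entry) or 38 to 45 weeks (naïve), and one added urine test brings the longest interval to 26 weeks nominal.

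Two stronger readings should be resisted. A reader might take 38 to 47 weeks as the expected exposure of a pregnancy. It is only the limit of the test schedule; a pregnancy begun soon after Visit 4 would normally be noticed earlier. A reader might also take the mean waits (19.0 to 23.5 weeks now, 10.8 to 11.9 with Visit 9) as upper bounds. They are not. Ignoring clinical detection pushes them up, but the assumption of uniform timing can err either way, and conceptions concentrated just after Visit 4 would give a mean wait near the full interval. They are illustrations only.

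The conclusion rests on nominal visit weeks and on girls who stay in Part 1 to Visit 15, since early termination brings the test forward. It concerns the safety of post-menarcheal girls and has no bearing on efficacy, alpha or power.

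**What to change.** In Sections 6.9.1.1 and 7.4.1 and Appendices 1.1 and 2.2, add a urine pregnancy test at Visit 9 (Week 26) for girls who have reached menarche.

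The cost is one urine hCG per eligible girl. The test is already in Table 2, and Visit 9 is an existing clinic visit with a urine drug screen, so no extra visit or routine blood draw is needed. The protocol does not say whether the drug-screen sample can be shared; if not, a second urine sample is taken at the same visit. A rare false positive would need a confirmatory test. The change requires a protocol amendment with IRB/IEC approval and helps only girls who have not yet passed Visit 9.
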